## **Appendix 2 Subject Diary Script**

## Subject Diary Script

### Subject Daily Diary Questions

1. Did you take your study medication today?
  - a)  Yes  NoIf Yes;
  - b) Did you take the study medication at least 1 hour before or at least 2 hours after a meal?  Yes  No
2. Evaluate today's bowel movement frequency.
  - a)  Number of bowel movements today \_\_\_\_\_
3. Have you noticed any blood in your bowel movement?
  - a)  Normal = (*No blood*)
  - b)  Streaks of blood
  - c)  Obvious blood
  - d)  Mostly blood

**Note: That a bowel movement may consist of one or multiple stools; what one experiences in one visit to the toilet is classified as a bowel movement. For the rectal bleeding score, the worst score during the day is the one which will be recorded.**

### Bowel Movement (BM) Frequency (daily)

To determine the effect of medical therapy on your bowel movement frequency, we need you to define your "usual" non-ill state of health.

- What is your normal bowel movement frequency?

Each day during the trial you will assess your bowel movement frequency. This will be entered into your daily diary.

- What is your bowel movement frequency today?

### Rectal Bleeding Occurrence (daily)

Each day during the trial you will assess your rectal bleeding. This assessment should be based on your worst episode of bleeding that day. One of the four (4) choices below will be entered into your daily diary:

Have you noticed any blood in your bowel movement? For example:

- If you see NO blood on the bowel movement or in the toilet water or visible anywhere in the toilet, enter a bleeding score of 0.

- If you see only red streaks of blood on the surface of the bowel movement, enter a bleeding score of 1.
- If you see red streaks of blood on the surface of the bowel movement and/or in the toilet water and/or visible anywhere in the toilet, enter a bleeding score of 2.
- If your bowel movement is mostly or totally blood, enter a bleeding score of 3.

1.1 Definitions/ Abbreviations

1.1.1 Definition of Terms

Terms	Definitions
Clinical Response Score	Stool frequency and rectal bleeding subscale of Clinical and Endoscopic Response Score
Endoscopic Response Score	Flexible sigmoidoscopy findings subscale of Clinical and Endoscopic Response Score

1.1.2 Abbreviations

Abbreviations	Meaning of abbreviations in document
ADR	Adverse drug reaction
AE	Adverse event
ALT	Alanine aminotransferase
ANCOVA	Analysis of covariance
AST	Aspartate aminotransferase
ATC	Anatomical therapeutic chemical
BM	Bowel movement
CRP	C-reactive protein
ECG	Electrocardiogram
eGFR	Estimated glomerular filtration rate
GEE	Generalized estimating equations
GGT	Gamma glutamyl transferase
HBV	Hepatitis B virus
HCV	Hepatitis C virus
HIV	Human immunodeficiency virus
HRQoL	Health-related quality of life
IBDQ	Inflammatory bowel disease questionnaire
IMP	Investigational medicinal product
INR	International normalized ratio
ITT	Intention-to-treat
MAR	Missing at random
MedDRA	Medical dictionary for regulatory activities
MI	Multiple imputation
mITT	Modified ITT
MNAR	Missing not at random
OL	Open label
PGA	Physician's global assessment
PMM	Pattern mixture model
PP	Per protocol
PT	Preferred term

Abbreviations	Meaning of abbreviations in document
QD	Once daily
QTc	Corrected QT interval
SOC	System organ class
TEAE	Treatment-emergent adverse event
UC	Ulcerative colitis
US	United states
WBC	White blood cell
WHO-Drug	World health organization drug dictionary

2 Trial Objectives and Endpoints

2.1 Objectives

2.1.1 Primary objective

- To demonstrate efficacy of mesalamine 4 g extended release granules (sachet) once daily (QD) in the induction of clinical and endoscopic remission versus placebo in subjects with active, mild to moderate ulcerative colitis (UC)

2.1.2 Secondary objectives

- To evaluate the efficacy of mesalamine 4 g extended release granules (sachet) using the Clinical and Endoscopic Response Score and the Clinical Response Score subset
- To assess C-reactive protein (CRP) levels and fecal calprotectin levels
- To assess health-related quality of life (HRQoL) using the Inflammatory Bowel Disease Questionnaire (IBDQ)
- To assess the incidence and severity of adverse events (AEs) and abnormal laboratory values

2.2 Endpoints

2.2.1 Primary endpoint

The primary efficacy endpoint is the proportion of subjects with remission, defined by the Clinical and Endoscopic Response Score ([Table 1](#)) at Week 8 as a score of,

- 0 for rectal bleeding, and
- “0” or “1 with at least 1 point decrease from baseline” for stool frequency, and
- 0 or 1 for endoscopic score.

The endoscopic score will be determined by an independent central reader.

Table 1 Clinical and Endoscopic Response Score (0 – 9)

Components	Subscale	Severity	Score
CLINICAL RESPONSE (Subject's Symptoms)	Stool Frequency^a (daily)	Normal number of stools for subject	0
		1 to 2 stools more than normal	1
		3 to 4 stools more than normal	2
		≥5 stools more than normal	3
	Rectal Bleeding^b (daily)	No blood seen	0
		Streaks of blood with stool	1
		Obvious blood with stool	2
		Blood alone passes	3
ENDOSCOPIC RESPONSE (Objective Evidence of Inflammation)	Flexible Sigmoidoscopy Findings	Normal or inactive disease	0
		Mild disease (erythema, decreased vascular pattern, granularity)	1
		Moderate disease (marked erythema, absent vascular pattern, any friability, erosions)	2
		Severe disease (spontaneous bleeding, ulceration)	3

Adapted from: Schroeder et al. (1987)(1); Sninsky et al. (1991)(2); Modified by Ferring Group, 2014

- a. Each subject serves as his or her own control to establish the degree of abnormality of the stool frequency.
- b. The daily bleeding score represents the most severe bleeding of the day.

2.2.2 Key secondary endpoints

1. The proportion of subjects with remission in the primary endpoint and the Physician's Global Assessment (PGA) score of ≤1 (Modified Mayo) at Week 8
2. Time to cessation of rectal bleeding, defined as time in days from randomization to the first day of 3 consecutive days with a rectal bleeding score of 0, based on subject daily diary

2.2.3 Secondary endpoints

- The proportion of subjects with endoscopic improvement, defined as an Endoscopic Response Score of 0 or 1, with at least a 1 point reduction from baseline in the endoscopic score at Week 8
- The proportion of subjects in clinical remission at Weeks 2, 4, and 8, defined as a score of 0 for rectal bleeding and "0" or "1 with at least 1 point decrease from baseline" for stool frequency in the Clinical Response Score subset
- Time to normal stool pattern, defined as time in days from randomization to the first day of 3 consecutive days with a stool frequency score of 0, based on subject daily diary
- The change from baseline in rectal bleeding score at Weeks 2, 4, and 8, based on subject daily diary

- The change from baseline in serum CRP levels at Weeks 2, 4, and 8
- The change from baseline in fecal calprotectin levels at Week 8
- The change from baseline to each scheduled assessment for published and validated domain scores of the IBDQ
- Safety assessed by incidence and severity of AEs and abnormal laboratory values

3 Trial design

This is a randomized, double-blind, placebo-controlled, parallel-group, multicenter, international, phase 3 trial to investigate the safety and efficacy of mesalamine 4 g extended release granules (sachet) for the induction of clinical and endoscopic remission in subjects with active, mild to moderate active UC. Following completion of Visit 0/screening, the subjects will be randomized to a treatment group during Visit 1/baseline. Each subject will receive a total of 8 weeks of double-blind treatment with either:

- one mesalamine 4 g extended release granules (sachet) QD (4 g/day) OR
- one 4 g placebo sachet to match mesalamine extended release granules (sachet)

Dose will be administered QD at least 1 hour before or at least 2 hours after a meal at approximately the same time each day. The sachet will be emptied on the tongue and swallowed with at least 8 ounces (240 mL) of water. Following randomization, the first dose of investigational medicinal product (IMP) will be administered at the site during Visit 1.

Subjects will visit the trial site 4 times during the double-blind part of trial for safety and efficacy evaluations: baseline and Weeks 2, 4, and 8. On a daily basis, subjects will record clinical symptoms (stool frequency and rectal bleeding) in an electronic diary. The Clinical and Endoscopic Response Score assessments and PGA will be performed at screening/baseline and Week 8. After 8 weeks of treatment, subjects will be evaluated for remission, defined as a Clinical and Endoscopic Response Score of rectal bleeding score of 0 and stool frequency scores of “0” or “1 with at least 1 point decrease from baseline”, with an endoscopic score of 0 or 1. Whereas, subjects will have only a Clinical Response Score assessment at Weeks 2 and 4.

Subjects who discontinue during the double-blind treatment before Week 8 will complete the double-blind end-of-treatment assessments and will be treated via investigator’s decision with local standard of care.

Subjects who are found to be worse defined by an increased number of bowel movements [BM], blood in the stool, abdominal pain and distention, or clinically relevant changes in laboratory chemistry and/or hematology on or after Week 2 will be offered early escape during the trial before Week 8 and will be treated by local standard of care. Subjects who complete Week 8 but fail to meet the defined criteria for remission will be given an option to receive open-label treatment with

mesalamine 4 g extended release granules (sachet) for 8 additional weeks in the current trial. If subjects do not opt to receive the 8-week open-label mesalamine treatment, they will be treated by local standard of care. If subjects opt to receive the additional 8-week open-label mesalamine treatment, they will continue with daily diary entries and visit the trial site at 10 and 16 weeks, with only a Clinical Response Score assessment at Week 10, and a Clinical and Endoscopic Response Score assessment performed at Week 16 in order to determine the subject's eligibility for entry into the maintenance trial.

Flexible sigmoidoscopy/colonoscopy will be video recorded and transferred to the independent central reader. The details of the tools, recording, data transfer, and assessment will be documented in an Imaging Charter. If the local site's endoscopic reading determines the subject is ineligible, the subject will be screen failed. If the local site's endoscopic reading determines that the subject is eligible, the flexible sigmoidoscopy recording will be sent to the independent central reader for final determination of eligibility. A flexible sigmoidoscopy will also be performed at Weeks 8 and 16 as applicable. These recordings will be sent to the independent central reader for endoscopic endpoint scoring.

Subjects from either treatment group who meet the defined remission criteria after the 8 week double-blind treatment period will be allowed to enroll into a double-blind trial investigating maintenance therapy of mesalamine 2 g extended release granules (Study 000175). Those subjects who do not achieve remission after the 8 additional weeks of open-label treatment will not be enrolled into Study 000175 and will be treated with the local standard of care.

The schedule of trial procedures is presented in [Appendix 2](#).

3.1 General Design Considerations

This trial is designed as a randomized, double-blind, placebo-controlled trial with 8 weeks of treatment. Subjects who achieve remission after the 8-week treatment will be allowed to enroll into a maintenance trial (Study 000175). To increase the number of subjects who continues to the maintenance trial from the current trial, an additional 8-week open-label mesalamine treatment period will be offered to subjects who complete Week 8 but fail to meet the defined criteria for remission.

The endoscopic score will be determined by an independent central reader.

3.2 Determination of Sample Size

The true remission rates at Week 8 for mesalamine 4 g extended-release granules (sachet) and placebo regimens were assumed as 36% and 18%, respectively, based on Kamm et al. (2007)(3), Lichtenstein et al. (2007)(4), and Marteau et al. (2005)(5). Under these assumptions, a sample size of 110 randomized subjects per group will provide at least 85% power to detect a statistically significant treatment group difference in the remission rate at a two-sided 0.05 significance level using the chi-square test.

4 Subject Disposition

The number of screened subjects will be summarized, and for subjects not randomized, the primary reason for exclusion from randomization will be summarized.

The number and percentage of subjects who are randomized, are treated with IMP, prematurely discontinued, and completed the double-blind period of the trial will be summarized with the reason of premature discontinuations. Similar summaries will be made for subjects who are enrolled to the 8-week open-label period.

The time to discontinuation will be summarized by the Kaplan-Meier estimates, and the treatment group difference will be tested by the log-rank test. In addition, reason-specific discontinuation will be summarized by the cumulative incidence estimates.

5 Protocol Deviations

The following protocol deviations will be identified as major protocol deviations:

- Overall IMP compliance of less than 80% during the double-blind period
- Not taking the randomized IMP
- Taking prohibited medications during the double-blind period

The final definition of major protocol deviations will be determined prior to breaking the blind.

The number and percentage of subjects with protocol deviations will be summarized.

6 Analysis sets

For each analysis set, the number and percentage of subjects excluded from it will be summarized by the reason of the exclusion.

6.1 Intention-To-Treat Analysis Set

The intention-to-treat (ITT) analysis set includes all randomized subjects. Analyses for the ITT analysis set will be conducted according to the randomized treatment regardless of the actual treatment received.

6.2 Modified Intention-To-Treat Analysis Set

The modified intention-to-treat (mITT) analysis set includes all randomized subjects who receive at least one dose of IMP. Analyses for the mITT analysis set will be conducted according to the randomized treatment regardless of the actual treatment received.

6.3 Per Protocol Analysis Set

The Per-protocol (PP) analysis set includes all randomized subjects who receive at least one dose of IMP and who do not have any of the major protocol deviations defined in Section 5.

6.4 Safety Analysis Set

The safety analysis set includes all subjects who receive at least one dose of IMP. Safety analyses will be conducted according to the treatment actually received.

7 Trial population

7.1 Demographics and Other Baseline Characteristics

Descriptive statistics of demographics and other baseline characteristics will be presented for all subjects in the ITT, PP, and safety analysis sets by treatment group unless otherwise specified.

Categorical data will be summarized using numbers and percentages. The percentages will be based on the total number of subjects with a corresponding assessment. Continuous data will be presented using the number of subjects, mean, standard deviation, median, minimum, and maximum.

7.1.1 Demographics

Baseline demographics and other baseline characteristics will be summarized by treatment group.

7.1.2 Disease Characteristics

Baseline disease characteristics (e.g., time since diagnosis of UC, extent of disease) will be summarized by treatment group.

Baseline Clinical and Endoscopic Response Scores will be summarized by treatment group.

7.1.3 Laboratory Efficacy/Pharmacodynamic Parameters at Baseline

Baseline serum CRP and fecal calprotectin levels will be summarized by treatment group.

7.2 Medical History

Medical history will be coded by system organ class (SOC) and preferred term (PT) using the Medical Dictionary for Regulatory Activities (MedDRA) version 17.1 or later and summarized by SOC (in alphabetical order), PT (in decreasing order of frequency), and treatment group for the ITT and safety analysis sets.

7.3 Prior and Concomitant Medication

Prior and concomitant medications will be coded by the Anatomical Therapeutic Chemical (ATC) classification system and preferred drug name using the World Health Organization Drug Dictionary (WHO-Drug).

Prior and concomitant drug usage will be summarized by ATC classification 1st level (alphabetically), ATC classification 2nd level (in decreasing order of frequency) and treatment group for subjects in the ITT and safety analysis sets. These medications will be tabulated separately for:

- 1) Prior medication; i.e. medication taken exclusively prior to treatment (i.e. with stop date before date of first IMP administration);
- 2) Concomitant medication, i.e. medication taken during the treatment period (i.e. medication that was not stopped before date of first IMP administration or started on or after the first IMP administration)

If the timing of the dose of a concomitant medication cannot be established in relation to the administration of IMP, it will be considered as concomitant medication.

Concomitant medications used during the double-blind period will be identified.

7.4 Physical Examination

Subjects with abnormalities at any screening, baseline, or post-baseline visit will be listed with all physical examination evaluations.

8 Exposure and Treatment Compliance

8.1 Extent of Exposure

The length of the treatment, calculated as (last dose date – first dose date + 1), will be summarized by treatment group for the safety analysis set. The summaries will be made for the double-blind period only, open-label period only, and combined double-blind and open-label periods. The combined summary will be made only for the exposure to mesalamine.

Following categorical summaries will be made for the double-blind period only:

- < 14 days, 14 - < 28 days, 28 - <42 days, 42 - <56 days, and 56 days or more
- At least 1 day, at least 14 days, at least 28 days, at least 42 days, and at least 56 days

8.2 Treatment Compliance

The overall compliance during the double-blind period will be calculated as number of days with IMP intake based on the daily diary data divided by the number of days that the subject is supposed to take the IMP during the treatment period. It will be summarized for the safety analysis set.

9 Efficacy

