### **5.6.2 Assessment of Compliance**

At Weeks 2, 4, and 8 (or at early withdrawal) during the double-blind treatment period, and at Week 16 during the open-label period, subjects will bring their unused IMP back to the trial site. Subject compliance will be assessed with a medication count by the investigator or coordinator at the end of the visit and will be documented.

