### **7.1.3 Subject Daily Diary**

The subject daily diary will be completed by the subject every evening starting the day of randomization (Visit 1/Day 1). Subject diary will consist of questions regarding IMP daily intake, stool frequency, and presence of blood content. The score for stool frequency and rectal bleeding will be calculated as an average based on scores collected from 3 day subject recall at Visit 0 or from subject diary data 5 days prior to Visits 2, 3, 4, 6 and 7 (see [Appendix 2](#)). If a subject recorded fewer than 3 days of scores during this 5-day period, the average score will be considered missing.

The subject daily diary and questionnaire will be completed via a validated Interactive Voice Response system (IVRS). Instructions on the use of the subject daily diary and questionnaire will be provided to each trial center.

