### 9.3 Protocol Deviations

The following protocol deviations will be identified as major protocol deviations:

- Overall IMP compliance of less than 80%
- Not taking the randomized IMP
- Taking prohibited medications

The final definition of major and minor protocol violations will be determined prior to breaking the trial blind.

The number and percentage of subjects with major protocol deviations will be summarized.

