#### **9.7 Extent of Exposure and Treatment Compliance**

The length of the treatment, calculated as (last dose date – first dose date + 1 day), will be summarized by treatment group for the safety analysis set.

The overall compliance during the double-blind period will be summarized for the safety analysis set.

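### Is per-protocol membership left undefined because SAP 8.2 does not spell out blank diary evenings, days after an early stop, or the choice of diary over medication count?

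*SAP*

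**What the plan says.** SAP 8.2 gives the compliance measure in one sentence: the "number of days with IMP intake based on the daily diary data divided by the number of days that the subject is supposed to take" study drug, restricted to the treatment period. SAP Section 5 lists "Overall IMP compliance of less than 80% during the double-blind period" as a major protocol deviation, and SAP 6.3 limits the PP set to dosed subjects "who do not have any of the major protocol deviations defined in Section 5". The ratio in 8.2 therefore decides PP membership.

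The protocol mentions compliance in several places:

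- Section 5.6.2 describes a site procedure: "Subject compliance will be assessed with a medication count by the investigator or coordinator at the end of the visit".
- Section 7.1.3 makes drug intake part of the diary: "Subject diary will consist of questions regarding IMP daily intake, stool frequency, and presence of blood content". The script in Appendix 2 asks each evening "Did you take your study medication today".
- Section 9.3 sets the same 80% threshold without naming a data source.
- Section 9.7 says only that "The overall compliance during the double-blind period will be summarized for the safety analysis set", with no formula.

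Protocol 9.3 and SAP Section 5 both leave the final definition of major deviations to a step before the blind is broken. Protocol 9.4 says the same of assignment to analysis sets.

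**The concern.** A set defined by a threshold needs a ratio that two programmers would compute identically. Three points seemed to stand in the way.

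1. **Blank evenings.** Neither document says in words what a day without a diary entry means for compliance. The rule requiring at least 3 scored days out of 5 covers only the stool and bleeding scores.
2. **Early stop.** The denominator could run for the planned 8 weeks (protocol synopsis, Duration of Treatment) or end when the subject stops. SAP 8.1, just before the formula, measures treatment length from first to last dose.
3. **Source.** Sites assess compliance by medication count, the SAP uses the diary, and SAP Section 12 declares no departure from the protocol's analysis.

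The second point is the one that could matter. Early escape from Week 2 is for subjects who worsen, and SAP 9.2.1 counts anyone who discontinues before Week 8 as a non-remitter. One reading keeps such subjects in the PP analysis as failures; the other removes most of them. An unwritten convention tied to outcome could move the PP estimate.

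**Working it through.** **Inputs.** Threshold 80% (SAP 5); planned treatment 8 weeks = 56 days (protocol synopsis); Visit 5 at Day 57 ±3 (protocol Table 1); assumed remission 36% and 18% with 110 per group (SAP 3.2). Neither document gives an expected early-stop rate or a rate of blank diary evenings.

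**The plan's own figure.** The compliance rule carries no computed figure. The remission rates used below come from the sample-size statement, which reproduces. With mean rate 0.27, the null standard error is √(2 × 0.27 × 0.73/110) = 0.0599 and the alternative one is √((0.36 × 0.64 + 0.18 × 0.82)/110) = 0.0586. Power is Φ((0.18 − 1.96 × 0.0599)/0.0586) = 85.7%, against a stated minimum of 85%.

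**Threshold in days.** 0.80 × 56 = 44.8, so 45 intake days are needed: 45/56 = 80.4% stays and 44/56 = 78.6% goes.

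**Blank evenings.** The numerator counts days on which the diary shows intake, and a blank evening shows none. The denominator counts days on which a dose was due, whether or not the diary was filled in. Taken as written, a blank is a day without intake. A fully dosed completer then leaves the PP set at 12 blanks (44/56 = 78.6%) and stays at 11 (45/56 = 80.4%). Dropping the blanks (44/44 = 100%) would depart from the formula. The rule is strict, but it is determinate.

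**Early stop, every dose taken and recorded.**

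| Doses before stop | Against 56 planned days | Against days to the stop |
|---|---|---|
| 14 | 25.0% | 100% |
| 28 | 50.0% | 100% |
| 42 | 75.0% | 100% |
| 44 | 78.6% | 100% |
| 45 | 80.4% | 100% |

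The two readings differ for every otherwise adherent subject who stops after 44 or fewer doses. They are not equally supported. The formula refers to days on which the subject was meant to take drug, not to 56 days. Under protocol 3.1.1, a subject who discontinues or takes early escape passes to local care and is no longer meant to take it. The 8-week sentence in the synopsis describes planned duration and does not mention compliance.

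**End date for completers.** This too is unstated and matters only at the margin: 45 intake days are 80.4% of 56, 78.9% of 57 and 75.0% of 60.

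**Source.** SAP 8.2 names the diary. Protocol 9.3 and 9.7 name nothing, and protocol 7.1.3 and Appendix 2 collect intake in the diary. The SAP therefore fills a space the protocol's statistical section left open, and Section 12 is not contradicted. A missing rationale does not make the ratio ambiguous.

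**Possible effect on the PP odds ratio (illustration).** Assume a fraction d of an arm stops after 44 or fewer doses, that all of them are non-remitters, and that nobody else is excluded. Removing them changes the arm's rate p to p/(1 − d).

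| Stopping early, mesalamine / placebo | Rates after removal | Odds ratio |
|---|---|---|
| all kept | 0.360 vs 0.180 | 2.56 |
| 10% / 10% | 0.400 vs 0.200 | 2.67 |
| 20% / 20% | 0.450 vs 0.225 | 2.82 |
| 10% / 20% | 0.400 vs 0.225 | 2.30 |
| 10% / 25% | 0.400 vs 0.240 | 2.11 |

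The shift goes either way and depends entirely on the assumed stopping pattern. No direction of bias follows.

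**The case for a change.** The strongest case for a change rests on the early stop. Early escape is a designed path, it depends on how the subject is doing, and both denominators can be traced to some text in the documents. The PP analysis exists to test robustness, which calls for a membership rule that can be reproduced. Postponing the definition until just before unblinding says when the rule will be fixed, not what it will be. Nor does the prohibited-medication deviation clearly close the gap: it applies during the double-blind period, and treatment begun after a subject has stopped may fall outside that. Finally, diary gaps did occur. SAP 9.1 reports subjects with too few entries before Visit 4 and repairs the scores, but says nothing about compliance.

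Part of this stands. The end of the denominator is unwritten, and it can decide whether a subject is in the PP set. But the objection identifies a missing detail; it does not show that a stated rule gives a wrong result. Either convention would be acceptable once recorded, and each has a cost: ending at the stop keeps very short exposures in the PP set, while using 56 days takes treatment failures out. The diary gaps are real, but the formula as written already deals with them, strictly.

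**Conclusion.** No change to the plan follows. Of the three points, two do not leave membership open: the source is named, and a blank evening counts as no intake under the formula as written. The third is a narrow gap that an analyst would sensibly fill by ending the denominator when the subject is no longer due study drug, with an equally simple choice of end date for completers.

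The reach is small. The PP set serves one sensitivity analysis of the primary endpoint (SAP 9.2.2) and baseline tables; the ratio also feeds the deviation counts and the compliance summary. The primary and key secondary analyses use the ITT set (SAP 9.2.1 and 9.3.1) and cannot be affected. Finalising deviation definitions and set membership before unblinding is already planned, so the convention can be recorded then without knowledge of treatment.

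This conclusion assumes that the planned step takes place and that one end date is applied to all subjects. The number of subjects affected cannot be computed, because the documents give no rates of early stopping or blank entries; the odds ratios of 2.11 to 2.82 around 2.56 illustrate assumed rates and are not forecasts.
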